Development of a Behavioral Intervention for Chronic Pain in Individuals With HIV
NCT02824562

STUDY PROTOCOL

Version 1.0
Sep, 2017

Send Questions or Comments to:
[name] [contact]
[name] [contact]

I. STUDY OVERVIEW

Defined as pain lasting longer than three months, chronic pain affects up to 30% of the US population. It often occurs in patients with complex chronic illness, including medical, psychiatric, and substance use comorbidities. However, chronic pain is not simply a symptom of these comorbidities. Its distinct neurobiologic basis and substantial impact on physical and emotional function make it a serious illness in itself. In recognition of its importance, the Institute of Medicine has called chronic pain a “public health crisis,” and identified research on chronic pain, particularly in populations most burdened by this condition, to be a priority.

The burden of chronic pain in HIV-infected patients is substantial. Prevalence estimates of chronic pain in HIV-infected patients are as high as 39-85%. Mounting evidence suggests that chronic pain in HIV is often associated with psychiatric illness, especially mood disorders such as depression, and has serious health consequences, including up to 10 times greater odds of functional impairment.

Non-pharmacologic, behavioral interventions to decrease pain and improve physical and emotional function in HIV-infected patients with chronic pain are needed. A consensus panel identified pain, physical, and emotional function to be the most important outcomes of chronic pain interventions. Commonly used pharmacologic therapies, including opioids, often do not result in substantial improvement in these outcomes, and carry risks including misuse, abuse, and addiction. In HIV, opioids may

actually be associated with worse pain, and adversely interact with antiretrovirals. Behavioral interventions are among the most effective and safe non-pharmacologic treatments for chronic pain in the general medical population.

II. OBJECTIVES

In this study we will conduct a two-arm pilot randomized controlled trial of the chronic pain behavioral intervention to investigate feasibility, acceptability, and when possible, preliminary impact.

III. STUDY ACTIVITIES

a) STUDY POPULATION

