A total of 40 patients (up to 60) who are patients at the UAB 1917 clinic, enrolled in CNICS, experiencing chronic pain (Brief Chronic Pain Screening Questionnaire (BCPQ) = at least moderate pain for at least 3 months) and moderately severe and impairing chronic pain (PEG pain questionnaire = average of all three times is 4 or greater).

Inclusion Criteria

1. Enrolled in CNICS
2. Age \geq 18 years
3. Chronic pain (Brief Chronic Pain Screening Questionnaire (BCPQ) = at least moderate pain for at least 3 months)
4. Moderately severe and impairing chronic pain (PEG pain questionnaire = average of all three times is 4 or greater)

Exclusion Criteria

1. Do not speak or understand English
2. Are planning a new pain treatment like surgery

3. Cannot attend the group sessions

Recruitment of participants will take place in the 1917 clinic. Participants will be recruited via word-of-mouth by clinic staff or providers, calls generated from flyer tear-offs, and responses to the flyer on the TV monitors.

b) PRE-SCREENING

Potential participants will be prescreened over the phone using our prescreening phone script. If the individual passes the telephone prescreen, he or she will be scheduled for an in-person pre-screening visit by a member of the STOMP recruitment team. The date and time of the pre-screening visit along with the participant contact information and preferred method of contact will be recorded on the Prescreening Visit Appointment Form. About 48 hours prior to the in-person prescreen visit, a reminder call from the research staff will be made to remind the potential participant of the prescreening visit. On the day of the prescreen, the research staff member conducting the prescreen will log onto Redcap and establish a unique RedCap instance for this participant and complete the prescreen section only. At the end of the prescreen, the research tech will record the participant's eligibility on the Prescreening Visit Appointment Form. If the participant is eligible for enrollment, a Screening and Enrollment Visit will be scheduled and recorded on a Screening and Enrollment Visit form. The participant will also be thanked and given their \$25 incentive.

If the participant is not eligible, he or she will be thanked for their time and give their \$25 incentive.

c) SCREENING AND ENROLLMENT

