The Screening and Enrollment Visit will be scheduled approximately 2-4 weeks from the date of the pre-screen visit and recorded on a Screening and Enrollment Visit form. Participants will receive a reminder call at about a week and 48 hours prior to the scheduled screening visit. At the beginning of the screening and enrollment visit, the participant will complete the informed consent process.

Informed Consent Procedures

Informed consent will be administered by staff trained in accordance to the University of Alabama at Birmingham Institutional Review Boards guidelines for obtaining informed consent. The staff member obtaining consent must verify the following: protocol name, version number, dates for use, and institution. The Study team member will also ensure that the most recent informed consent is being used for the study. Initial informed consent must be completed and documented before any other study related procedures are done.

Comprehension will be assessed by asking the participant to summarize the study activities or some general open ended questions will be asked like what can you tell me about this study, can you tell me about how long the study may last, etc.

The consent process is estimated to take around 30 minutes.

Study staff will ensure that the participant has signed and dated the consent form including the HIPAA form.

All signed consent forms will be stored in locked file cabinets under respective participant files.

Baseline Assessment

The research staff will then administer the baseline assessment which includes a confirmatory set of screening questions via RedCap. Confirmation of the participant's eligibility will be recorded in RedCap.

Following completion of the baseline assessment, participants will be thanked for coming and given their \$50 incentive payment for their time. Completion of Baseline assessment will be recorded in excel logs.

d) RANDOMIZATION

Our team will utilize a 1:1 ratio for allocation to the treatment and control arms at each participating site. The UAB statistician will generate a list of random arm assignments for each site. Randomization list will be provided to the study coordinator to create sealed envelopes with participant ids on it in chronological order.

Once the participant completes the enrollment procedures, study staff will open the sealed envelope and will show the random arm assignment to participant and record it in the excel logs.

e) ASSIGNMENT OF ARM OF STUDY

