Approximately, 20 intervention arm and 20 control (standard of care) participants will be randomly assigned. Recruiting staff and research personnel will be masked to treatment arm assignment at the initial study visit. After the initial study visit, study coordinator will inform the participant of the follow-up assessments and thank the participant for their time. Staff personnel doing the assessment will still be blinded to the arm assignment.

If the participant is randomized to the intervention group, the participant will be informed of the next steps which includes the first group session. If the date of the first group

session has been established, the participant will be informed of the date and time. If it has not been scheduled, the participant will be informed that s/he will receive a call within the next two weeks informing his/her with the date and the time of the first group session

f) INTERVENTION

This behavioral intervention consists of 12 intervention sessions (6 group and 6 individual sessions). The sessions will be completed over a period of 12-16 weeks from enrollment. The first intervention session will be a group session for all participants followed by individual and then alternating group and individual session for the rest of the sessions.

Group intervention Sessions

A total of 6 group sessions will be conducted over a period of 12-16 weeks from study enrollment date. These sessions will be led by a peer. A peer is an HIV-infected patient of the UAB 1917 Clinic living with chronic pain, who has completed all ten of the one-on-one sessions offered, received training to co-facilitate the six group sessions with the interventionist, and is successfully self-managing his/her chronic pain.

Participants will receive a reminder call/text approximately 48 hours before the group session to remind them of the upcoming session. Participants will also be notified of the upcoming group sessions at the end of each one-on-one intervention. Group sessions will be conducted in UAB 1917 clinic building or the Bevill Biomedical Research Building (BBRB). A sign-in sheet will be used to document attendance. Session notes will be used to document any major issues presented or any anecdotal nuances identified. The date, start time and end time of the session will also be documented. Participants will

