All participants in the intervention group will also receive a baseline, post-intervention (after all sessions are completed), and at about 3 months (1 month leeway) assessment. These may be conducted by phone or in person. They will also participate in an audio-recorded in –person qualitative interview at the mid-point and end of the trial which will be transcribed using a third party company.

Qualitative interviews

Participants assigned to intervention arm, peers and interventionists of the study will be interviewed at mid-point of the study and end of the study to provide their feedback on the STOMP intervention. These interviews will be audio-recorded and later transcribed using third party.

g) CONTROL

The control group will receive “treatment as usual”. The “treatment as usual” or control arm refers to the standard of care that patients receive at the UAB 1917 clinic. This standard of care is for patients to discuss chronic pain with their providers at their

discretion. Although highly variable, providers can recommend and prescribe pharmacologic (e.g., opioid and other pain medication), non-pharmacologic (e.g., physical therapy, referral to psychology) approaches for pain. This study will not interfere in any way with usual care. No additional treatment will be provided to participants allocated to the control group. The control group participants will complete the baseline assessment and around 12 week follow-up (1 month leeway) assessment.

h) SNAP SHOT OF STUDY ACTIVITIES

Procedure	Length of Time Required of Participants	Frequency of Repetition
Individual sessions (intervention group only)	6 sessions, up to approx. 120 minutes each	Maximum of on average every other week
Group sessions (intervention group only)	6 sessions, up to 120 approx minutes each	Maximum of on average every other week
Questionnaire assessments – see attached	Approx 30 minutes	Baseline, end of intervention, and 3 months after intervention
Qualitative interviews (intervention group only)	Approx up to 120 minutes	Midpoint and end of trial
Phone calls (intervention group only)	Approx up to 30 minutes	Average of once weekly

h) SUMMARY OF COMPENSATION

Intervention group

In person for Prescreen	\$25
Screening/Enrolment visit	\$50
Mid-point qualitative interview	\$50
End of study qualitative interview	\$50
Post intervention follow up	\$50
3 month follow up	\$100

Control group

In person for Prescreen	\$25
Screening/Enrolment visit	\$50
12 week assessment	\$50

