3 month follow up	\$100

Offer parking vouchers/coffee vouchers/bus tickets etc. as required to the participants if that is the standard practice followed over at the clinic.

IV. DATA COLLECTION AND MANAGEMENT

All study documentation will be kept in locked file cabinets in BBRB or CCB in study personnel's offices. RedCap database can only be accessed by STOMP personnel using a UAB computer or encrypted laptop.

V. DATA ANALYSIS

Outcomes were reported as means and standard deviations for continuous variables, and frequencies and percentages for categorical variables. T-tests were used to compare change scores for continuous variables and Fisher's exact

tests were used to compare percentages. Interviews were analyzed thematically by two independent coders. Discrepancies were reconciled, a code book was created, and the lead analyst coded the remaining transcripts with continued input from the other coder. Representative quotes are presented for themes that helped us understand why and how the intervention could work.

VI. CRISIS PROTOCOL

As a general note, referrals can be made for crisis consultation at any time. The research staff will document the findings of his/her evaluation and the course of action taken. Providers for the patient may be informed about the same.

VII. PROTECTION OF HUMAN SUBJECTS

Our team has devised a comprehensive plan for ensuring protection of human subjects throughout the course of the proposed study. We will utilize an English-language consent form with common phrasing that describes that no special privileges or considerations will be conferred as a result of study participation, and that access to medical care will not be affected by the potential participant's decision to enroll in the study. The procedures listed in the following sections detail procedures that have been approved and utilized during recent years of clinical and behavioral trials at each site for collaborative research that utilizes sensitive information from participants. Our team will make every effort to protect all participants' confidential and private information in order to minimize possible study-associated risks.

All findings related to this research will be available and provided to study participants in accordance with standard practices. Clinical and measurement data used for research studies will be released only in de-identified fashion.

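### Continuous outcomes are compared by t-tests on change scores, which fix the baseline slope at 1; ANCOVA on the baseline already collected would usually be more precise and would remove the over-correction of chance imbalance.

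*Combined protocol and SAP*

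**What the plan says.** Section V (Data analysis) reports continuous outcomes as means and SDs and then states: "T-tests were used to compare change scores for continuous variables". Percentages are compared by Fisher's exact test. No regression, mixed model or ANCOVA appears in the protocol. The only use of baseline is the subtraction inside the change score.

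Four other places bear on this:

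- **Objectives (section II).** The pilot is "to investigate feasibility, acceptability, and when possible, preliminary impact".
- **Size (sections III.a and III.e).** The planned total is 40, with a ceiling of 60; "Approximately, 20 intervention arm and 20 control (standard of care) participants will be randomly assigned".
- **Timing of baseline (sections III.c and III.d).** At the enrolment visit, "The research staff will then administer the baseline assessment which includes a confirmatory set of screening questions via RedCap". Allocation comes afterwards: "Once the participant completes the enrollment procedures, study staff will open the sealed envelope".
- **Entry on a pain score (section III.a).** Patients must have a PEG average of 4 or more. PEG is the only pain severity score named, and only as an entry criterion; the outcome questionnaires are described as attached and are not in the document.

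**The concern.** A t-test on follow-up minus baseline is a linear model in which the baseline coefficient is set to 1 instead of being estimated. Symptom scores usually have a slope below 1, and selecting patients on a high score makes regression to the mean more visible. Two things follow when the slope is below 1:

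- The arm that happens to start worse shows the larger fall even if the intervention does nothing, so the estimate in a given sample moves with chance imbalance in that outcome's own baseline.
- The comparison carries noise that the collected baseline could remove.

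This matters because preliminary impact is an objective, these t-tests are the only between-arm comparison stated for continuous outcomes, and with about 20 per arm chance imbalance is large. What is at stake is the precision and stability of the impact estimate. Validity is not in question.

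**Working it through.** The plan states no alpha, power, effect size, SD or correlation, so it has no figure of its own to reproduce. From the documents: n = 20 per arm (N = 40), or n = 30 per arm at the ceiling of 60. Assumed: two-sided 5%, an effect of 0.5 SD, a common slope, normal data and complete follow-up.

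**Formulas.** Let b be the slope of follow-up on baseline, σx² the baseline variance and σe² the residual variance. Per-patient variances are:

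- change score: σe² + (1 − b)²σx²
- ANCOVA: σe² × (N − 3)/(N − 4), where the last factor is the cost of estimating b: 37/36 = 1.028 at N = 40 and 57/56 = 1.018 at N = 60.

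With unit variances at both times, b equals the correlation r, and these become 2(1 − r) and (1 − r²) × cost. The ANCOVA/change ratio is cost × (1 + r)/2.

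**Equal variances, 20 per arm** (power from the noncentral t):

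| r | Change variance | ANCOVA variance with cost | Ratio | 40 patients match | Power, change | Power, ANCOVA |
|---|---|---|---|---|---|---|
| 0.3 | 1.40 | 0.935 | 0.67 | 60 | 26% | 36% |
| 0.5 | 1.00 | 0.771 | 0.77 | 52 | 34% | 42% |
| 0.7 | 0.60 | 0.524 | 0.87 | 46 | 51% | 57% |
| 0.9 | 0.20 | 0.195 | 0.98 | 41 | 93% | 94% |

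The ratio reaches 1 at r = 2/1.028 − 1 = 0.946; above that ANCOVA is very slightly worse. At 30 per arm the ratios are 0.66 / 0.76 / 0.87 / 0.97, and power at r = 0.5 goes from 48% to 59%.

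**Over-correction.** Given a baseline difference D between arms, the change-score estimate shifts by (b − 1) × D. For D = 0.3 SD the size of the shift is 0.21, 0.15, 0.09 and 0.03 SD at b = 0.3, 0.5, 0.7 and 0.9. The standard error of D is √(2/20) = 0.316 SD, so the chance of a difference above 0.3 SD in either direction is 34%. At 30 per arm it is 25%.

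**Error rate by simulation** (no true effect, 20 per arm, 40,000 trials per setting). Overall, both tests reject about 5% of the time. Split by imbalance, at r = 0.3 / 0.5 / 0.7 / 0.9:

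- above 0.3 SD: change score 9.9 / 8.8 / 7.0 / 5.4%, ANCOVA 5.2 / 5.0 / 4.8 / 4.8%
- 0.3 SD or less: change score 2.4 / 3.2 / 3.9 / 4.7%

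The change-score test is therefore liberal in the imbalanced third of trials and conservative in the rest, averaging 5%.

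**PEG selected at 4 or more.** The inputs are assumed values *before* selection: mean 5 to 6, SD 2 to 2.5 at both times, correlation 0.5 to 0.6, with no upper limit on the score. Truncation at 4 shrinks the baseline SD to about 1.4 to 1.9 but leaves the slope at 0.5 to 0.6. The correlation among enrolled patients is then about 0.36 to 0.51.

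Example, with mean 5.5, SD 2.25 and r = 0.5:

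- σe² = 2.25² × 0.75 = 3.797, and the enrolled baseline SD is 1.642
- change variance = 3.797 + 0.25 × 1.642² = 4.471
- ratio = 3.797/4.471 = 0.849, or 0.873 with the cost; 40/0.873 ≈ 46

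Over the whole grid at 20 per arm, the ratio with cost is 0.85 to 0.92, 40 patients match about 43 to 47, and power rises by about 3 to 5 points. A 0.3 SD imbalance shifts the change-score estimate by 0.09 to 0.13 SD of follow-up. At 30 per arm the ratio is 0.84 to 0.91 and the gain about 4 to 7 points.

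**The case against.** The strongest reply is that nothing is broken. The test is unbiased and keeps its 5% rate, and this is a feasibility pilot with no power target, primary-outcome test or decision rule that depends on it. For PEG the gain is a few points on a base of about 34 to 39%, so the trial is underpowered for a 0.5 SD effect either way. The correlation is unknown, PEG may not be an analysed outcome, and section V is in the past tense, so the analysis may already be done.

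Most of this stands, and it limits the weight of the point:

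- The loss of precision is likely, not certain; it depends on the slope.
- Subtracting baseline is itself an adjustment. What is missing is one with an estimated slope.
- The raised rejection rates apply only to imbalanced samples and are offset by low rates in balanced ones.

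None of it supports keeping the change score as the main comparison. Over most of the plausible range ANCOVA is better, and where it is not, the loss is trivial. The pilot setting also argues for it, because small samples are where chance imbalance is largest.

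**Conclusion.** The point holds as a worthwhile, low-cost improvement to a valid analysis. On the equal-variance assumption, ANCOVA reduces the variance by about a third at a correlation of 0.3, 13% at 0.7 and 2% at 0.9. On the assumed PEG values it reduces it by 8 to 15%. The algebra is firm; the sizes rest entirely on assumed correlations, SDs and effect size, and on complete follow-up. The over-correction is conditional on the imbalance actually observed and is not a bias over repeated randomisation. Clustering by group session and missing follow-up are separate matters that neither analysis resolves.

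**What to change.** In section V, replace the change-score t-test as the between-arm comparison with ANCOVA: for each continuous outcome, a linear model of the follow-up value on assigned arm and the baseline value of the same outcome. Analyse participants in their assigned arm and report the adjusted mean difference with its 95% CI. Keep change scores as description.

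If the t-tests have already been run, leave them as reported, add the adjusted analysis and label it as added.

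State which follow-up each comparison uses. Section III.g describes one for controls: "The control group participants will complete the baseline assessment and around 12 week follow-up (1 month leeway) assessment". The activity table lists two follow-up questionnaires without limiting them to one arm, and the compensation list pays controls for both a 12-week and a 3-month assessment. These must be reconciled before any model uses both time points.

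The cost is one degree of freedom per model and no new data. It is a wording change if the analysis is still ahead, or one extra labelled analysis per outcome if it is not.

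### Only the intervention arm meets in groups, but the change-score t-tests treat participants as independent, so their standard errors may be too small by an unknown amount

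*Combined protocol and SAP*

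**What the plan says.** Section III(f) states: "This behavioral intervention consists of 12 intervention sessions (6 group and 6 individual sessions"). On their order it says: "The first intervention session will be a group session for all participants"; individual and group sessions then alternate. A peer leads the group sessions together with the interventionist. The activity table in Section III(h) limits group sessions to the intervention arm, and Section III(g) gives controls usual care and nothing further.

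On numbers, Section III(e) states: "Approximately, 20 intervention arm and 20 control (standard of care) participants will be randomly assigned". Section III(a) allows the total to rise from 40 to 60. Attendance at groups is documented: "A sign-in sheet will be used to document attendance".

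For continuous outcomes Section V, written in the past tense, says: "T-tests were used to compare change scores for continuous variables". That this compares the two arms is my inference. The section has no term for group, no ICC, no confidence interval and no significance level. The documents do not state how many groups there are, how large they are, or whether membership is fixed. Section II puts feasibility and acceptability first and makes preliminary impact conditional.

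**The concern.** Participants are randomised individually, but those in one arm then share sessions, leaders and each other's company. If that makes members of a group respond alike, the intervention-arm mean varies more than 20 independent people would imply. A two-sample t-test leaves this extra variance out. It also slightly underestimates the variance it does include, because people in the same group differ less from one another.

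The impact estimate would then look more precise than it is. A reader could not judge by how much, because the plan does not call for reporting the number and size of groups. Feasibility and acceptability results are unaffected.

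**Working it through.** The plan gives no sample-size calculation, SD, significance level or ICC, so it has no figure of its own to reproduce.

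**Inputs from the documents.** About 20 per arm (Section III(e)); up to 60 in total, so 30 per arm (Section III(a)); groups in one arm only (Sections III(f) to III(h)).

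**Assumptions.** Total variance 1 in each arm, fixed groups, full attendance, ICC from 0 to 0.10, groups of 5 to 10, and one group of 20 as the extreme. A two-sided 5% level is assumed for rejection rates.

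**Formulas.** Let n1 and n0 be the intervention and control arm sizes, and m = (sum of squared group sizes) / n1.

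- True variance of the difference: [1 + (m−1)ICC]/n1 + 1/n0.
- Variance the pooled t-test reports, on average: {[(n1−1) − (m−1)ICC + (n0−1)]/(n1+n0−2)} × (1/n1 + 1/n0).
- The SE multiplier is the square root of the first over the second. With n1 = n0 = n it reduces to sqrt{[2 + (m−1)ICC] / [2 − (m−1)ICC/(n−1)]}.

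**Numbers in, 20 per arm.**

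- Two groups of 10, ICC 0.10: (m−1)ICC = 0.90; sqrt[2.90/(2 − 0.90/19)] = sqrt(2.90/1.953) = 1.219.
- One group of 20, ICC 0.10: (m−1)ICC = 1.90; sqrt[3.90/(2 − 1.90/19)] = sqrt(3.90/1.90) = 1.433.

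The table gives the multiplier. In brackets is how often the ordinary t-test rejects a true null in simulation (200,000 runs per setting).

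| Groups | m | ICC 0.01 | ICC 0.05 | ICC 0.10 |
|---|---|---|---|---|
| four of 5 | 5 | 1.010 (5.3%) | 1.052 (6.2%) | 1.101 (7.4%) |
| 7, 7 and 6 | 6.7 | 1.015 (5.3%) | 1.073 (6.6%) | 1.142 (8.4%) |
| two of 10 | 10 | 1.023 (5.6%) | 1.113 (7.7%) | 1.219 (10.4%) |
| one of 20 | 20 | 1.049 (6.3%) | 1.230 (10.7%) | 1.433 (16.6%) |

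At ICC 0 the multiplier is 1. At 30 per arm, groups of 5 to 10 give almost the same values (1.05 to 1.11 at ICC 0.05, 1.10 to 1.21 at ICC 0.10). For groups of 5 to 10 at 20 per arm, multiplying the SE by the factor for the true ICC brings rejection back to 4.9% to 5.1%.

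**In interval terms.** The naive 95% half-width at 20 per arm is t(38) × sqrt(2/20) = 2.024 × 0.316 = 0.64 SD of change. For groups of 5 to 10 it becomes 0.67 to 0.71 SD at ICC 0.05 and 0.70 to 0.78 SD at ICC 0.10. For one group of 20 it becomes 0.64 × 1.230 = 0.79 and 0.64 × 1.433 = 0.92 SD.

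**Baseline adjustment, a separate matter.** With equal variances at the two times and baseline to follow-up correlation r, the adjusted SE divided by the change-score SE is sqrt[(1+r)/2]. For r = 0.3, 0.5 and 0.7 (assumed) this is 0.81, 0.87 and 0.92.

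**The case against.** The strongest reply is that this is a pilot. It makes no power claim and has no go/no-go rule, and a naive interval 2 × 0.64 = 1.28 SD wide says little about efficacy, clustered or not. That stands, and it is why the point is minor. It does not remove the point: the plan chose to run between-arm tests, and their stated uncertainty should be honest.

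Second, the size rests wholly on assumed group sizes and ICCs. That also stands. A reader might infer that the understatement is established as modest. The documents do not support that, because they give neither quantity: the same ICC of 0.10 yields 1.10 or 1.43 depending on group structure. Nor do they support the opposite inference, that all intervention participants form one group. The sentence "The first intervention session will be a group session for all participants" sets the order of sessions, not the number of groups. Section III(e) allows for a first session with no date yet, in which case "s/he will receive a call within the next two weeks"; that fits one group or several.

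Third, a reader might conclude that the plan's confidence intervals are wrong. Section V names none. The claim concerns the t-test's SE and p-value, and any interval derived from them.

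Fourth, one might extend the charge to Fisher's exact test, of which Section V says "tests were used to compare percentages". It too assumes independence, but it is conservative at this size. With groups of 5 to 10 and event rates of 20% to 50%, it rejects 2.0% to 2.5% of the time at ICC 0, 2.8% to 4.3% at 0.05 and 3.6% to 6.3% at 0.10. Its conservatism mostly absorbs the effect, so the point is confined to the t-tests.

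Fifth, membership may not be fixed. Letting up to half of sessions be attended with another group hardly changes rejection at ICC 0.10 (7.4% to 7.8% for groups of 5, 10.5% to 10.9% for groups of 10). Rolling entry was not examined, so the multiplier is approximate there.

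Finally, sign-in sheets already allow attenders to be placed. What is missing is the assigned group of non-attenders and a commitment to report the structure.

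**Conclusion.** The concern holds conditionally and is minor. The design is partially nested and the t-tests ignore it. With a positive ICC their standard errors and p-values are too small; with ICC 0 nothing is wrong. Under the assumptions above, the understatement runs from negligible (a multiplier of 1.01 for groups of 5 at ICC 0.01) to substantial (1.43 for one group of 20 at ICC 0.10). The documents do not show where in that range the trial lies. Only the preliminary-impact aim is touched. They do not support saying that the error rate is in fact inflated, or that the pilot's main results are unsound.

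**What to change.** 1. **Group membership.** Record each intervention participant's assigned group, including those who never attend. If data are already collected, reconstruct it from sign-in sheets and scheduling records and state who cannot be placed. Report the number and size of groups. Cost: one field and a check against existing records.

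2. **Sensitivity interval.** Report the between-arm difference with its ordinary confidence interval. Beside it, give an interval with the SE inflated over a stated ICC range, for example 0 to 0.10. Use the general multiplier above, which allows unequal arms; it assumes fixed groups and is approximate otherwise. If there is only one group, state that its effect is confounded with arm. With a handful of groups the ICC cannot be estimated usefully, so a stated range is preferable to a fitted value. Cost: a wider interval, by the multipliers tabulated above.

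3. **Precision, separately.** Replace the change-score t-test with a between-arm comparison adjusted for the baseline value already collected in both arms. Under the correlations assumed above, the SE falls to about 0.81 to 0.92 times the change-score SE, with no new data. This is not a remedy for clustering and should not be counted against the cost of step 2. If the step 2 multiplier is applied to the adjusted estimate, use the residual ICC and say that the result is approximate.
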